5.7 Withdrawal of Subjects

Participants will be free to leave the study at any time. If any participants leave the study before it is finished, there will be no penalty. Participants will not lose any benefits to which they may otherwise be entitled. If the participant chooses to tell the researchers why they are leaving the study, the reasons for leaving may be kept as part of the study record. The study team may continue to review the data collected prior to study withdrawal but cannot collect further information. If participants decide to leave the study before it is finished, they will notify the study primary contact.

Subjects may be withdrawn from the study for the following reasons: (1) the study team believes that it is not in the subject's best interest to stay in the study; (2) a subject displays disruptive behavior towards group members or staff; (3) a subject become ineligible to participate; (4) a subject's condition changes and they need treatment that is not allowed while you are taking part in the study; (5) subjects do not follow instructions from the researchers; (6) the study is suspended or canceled.

6.0 Reporting/Data Safety Monitoring Plan

We will report any unanticipated problems, serious adverse events, and protocol deviations to the AAVA IRB within 24 hours of their occurrence and we will follow standard operating procedures to ensure appropriate follow-up and resolution.

We will monitor A1c and lipid levels at 0, 6 months, and 12 months. Participants and their PCPs will be notified of laboratory test results. In the event that a participant's A1c is in the type 2 diabetes range, we will ensure that they have timely PCP follow-up to discuss management. Participants will be encouraged to inform the study team of any adverse events due to increased physical activity throughout the study period.

When following a low-carbohydrate diet, some individuals can experience an elevation in their LDL cholesterol levels. The cause for this elevation is not completely known. These results will also be communicated to PCPs. Depending on the degree of elevation, participants may be advised to start a cholesterol-lowering medication or to increase the dose if they are already taking a cholesterol medication. Participants may also be advised to modify their diet by increasing their intake of carbohydrates.

All paper data will be stored in locked cabinets accessible only to research staff in VA-vented space on the third floor of Building 16, North Campus Research Center. All electronic data will be stored in access-restricted study folders behind the VA firewall.

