We will obtain HbA1c and lipid levels at 6 months and 12 months. If these tests are abnormal, participants' PCPs will be notified via the electronic health record. Additionally, participants will be sent a letter informing them of their test results so that they can also arrange for appropriate follow-up care. This letter will be submitted with a future amendment prior to the start of study recruitment.

9.3 Indicate the level of risk you believe this protocol has: (The IRB will make the final risk level determination.)

- Minimal Risk
- Greater than Minimal Risk

9.4 Discuss benefits that may be gained by the subject as well as potential benefits to society in general. (see ? for guidance)

The risks of the intervention are minimal and side effects are completely reversible if an individual discontinues the low-carbohydrate diet. In contrast, there is a great potential benefit to this intervention, as the dietary advice may help study participants to lose weight and decrease their risk of type 2 diabetes.

9.5 Describe the availability of resources subjects may need as a consequence of their participation, including medical and mental health services (e.g. ER, hotlines, clinical staff available).

Study participants will be provided with the phone number of the PI to contact with any concerns raised

due to participation in the program.

9.6 Discuss why the risks to subjects are reasonable in relation to the anticipated benefits to subjects and in relation to the importance of the knowledge that may reasonably be expected to result.

The risks are minimal relative to the potential benefits. The probability and magnitude of risks of harm or discomfort anticipated in the research are not greater in and of themselves than those ordinarily encountered in daily life or during the performance of routine physical or psychological examinations or tests. In addition, the potential benefits of preventing type 2 diabetes is significant.

9.7 Briefly describe the procedures or explain why there is no need for established procedures for the orderly withdrawal or termination of participation in the protocol by the participants:

Participants will notify the study team if they desire to withdraw from the study. Study team members will explore and document reasons for withdrawal. No data will be collected from participants after they withdraw from the study. Data collected prior to their withdrawal will be used in analyses.

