The PI reserves the right to withdraw participants from the study for any of the following reasons:

- She believes that it is not in their best interest to stay in the study.
- They become ineligible to participate.
- They do not follow instructions.
- Their behavior toward the staff or other participants is disruptive or inappropriate.
- The study is suspended or canceled.

Please note that patients do not have to follow a low-carb diet to remain in the study. Weight loss is our measure of dietary adherence.

9.9 The procedures regarding reporting adverse events and protocol deviations/violations to the IRB should be described. If these are adequately described in your DSMP/DSMB, there is no need to duplicate the information here. In these cases, please attach a copy to the Initial Protocol Submission Form.

All serious adverse events, unanticipated problems, and protocol deviations will be reported to the IRB according to VAAHS policy. Please see narrative for DSMP.

9.10 The Principal Investigator and the Study Team will report all adverse event, complaints, problems and non-compliance according to this VAAHS policy and using the appropriate form (Adverse Event Reporting Form can be found in the upper right corner in the Help  Section). *Do not submit in AAROW. Please contact IRB Coordinator to discuss [name].****

Agree

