5.0 Study Procedures

5.1 Study Design

We will conduct a single-arm mixed methods pilot study to test the preliminary efficacy on weight loss of a LC-DPP among Veterans with prediabetes (as defined by the American Diabetes Association [ADA] ²⁴). We hypothesize that at least 50% of LC-DPP participants will achieve at least 5% weight loss at 12 months and that the average weight loss in the LC-DPP will be greater than the average weight loss among historical controls in VA MOVE!.¹¹

Our team previously adapted the Centers for Disease Control and Prevention's (CDC's) National Diabetes Prevention Program (NDPP) curriculum—a lifestyle change program similar to MOVE!—to teach participants to follow a low-carbohydrate rather than a low-fat diet. We pilot tested our low-carbohydrate Diabetes Prevention Program (LC-DPP) among adults with prediabetes at a single, academic medicine primary care clinic.

The LC-DPP curriculum was adapted from the CDC National Diabetes Prevention Program materials and consists of 16 weekly one-hour group sessions over first 6 months (i.e. core phase) and 8 one-hour group sessions once or twice a month over the next 6 months (i.e. maintenance phase). Importantly, our adapted curriculum will adhere to the CDC's Diabetes Prevention Recognition Program (DPRP) guidelines, which aim to maintain the integrity of the DPP in heterogeneous settings. The DPRP formally recognizes sites that achieve specific targets (e.g. session attendance, weight loss) through use of a CDC-approved curriculum. Therefore, our curriculum, if effective, may be eligible for CDC-approval, which would facilitate future dissemination of this intervention.

We will use a mixed-methods sequential explanatory design, which is to say that quantitative data and qualitative data will be collected in two consecutive phases within the study ²⁵. Specifically, in the first phase, we will collect and analyze the quantitative data (e.g. surveys, weight, A1c, lipids). In the second phase, we will collect and analyze qualitative data (e.g. semi-structured interviews). The rationale for this approach is that the quantitative data will provide a general overview of the intervention's efficacy and limitations, and the qualitative data will help to explain these findings by exploring participants' experiences and perspectives in more depth.

Intervention

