 - The researchers will minimize this risk by compensating participants for the time required to complete the surveys at 6 and 12 months and to complete blood draws at 0, 6, and 12 months.
- Blood draws:
 - Adverse effects of blood draw may include lightheadedness, dizziness, bruise or infection at blood draw site.
 - If participants experience any adverse effects, we will ensure that participants receive appropriate medical care

- Questionnaires:
 - Some of the questions may make participants feel uncomfortably or upset. All participants are free to decline to answer any questions they do not wish to answer and to discontinue participation at any time.
- Diet:
 - Participants may experience some side effects when first reducing the amount of carbohydrates in the diet. This may include constipation, headache, bad breath, and muscle cramps. These symptoms usually go away after the first couple weeks on the diet. Participants can speak with study staff and study physicians ([name]). We have also shared information with participants' primary care providers regarding the benefits and potential side effects of low-carbohydrate diets.
- Increase in physical activity:
 - Participants may experience harm or injury from exercise if they increase their physical activity as a result of participation. As there is no requirement for patients to engage in physical activity as part of this study and no physical activity will be encouraged other than that ordinarily encountered in daily life, we do not consider the risk to be above minimal. Participants will be encouraged to contact the study team and/or their PCP in the event of any adverse events.

As with any research study, there may be additional risks that are unknown or unexpected. We do not know if participants will get any benefits from taking part in this research study. However, possible benefits may include weight loss, decreased risk of diabetes, reduction in hemoglobin A1c. Participation in this study may also help the study team to design and test new ways to help more people prevent type 2 diabetes.

Participants will receive results of a hemoglobin A1c and cholesterol tests at 6 and 12 months.

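### The 24-hour safety reporting clock runs from occurrence rather than awareness, and no class includes a scheduled open question about adverse events

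*Protocol*

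**What the plan says.** The protocol narrative, section 6.0, sets the reporting rule: "We will report any unanticipated problems, serious adverse events, and protocol deviations to the AAVA IRB within 24 hours of their occurrence". The IRB application, section 9.9, covers the same three kinds of event but gives no number of hours: "All serious adverse events, unanticipated problems, and protocol deviations will be reported to the IRB according to VAAHS policy. Please see narrative for DSMP". Narrative section 8.0 again promises notification of the IRB, also without a time limit.

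On how the team hears of events, section 6.0 has one request to participants: "Participants will be encouraged to inform the study team of any adverse events due to increased physical activity throughout the study period". Elsewhere there are three further routes:

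- Narrative section 5.1, in the risk item on physical activity: "Participants will be encouraged to contact the study team and/or their PCP in the event of any adverse events".
- Narrative section 5.1, in the risk item on diet: "Participants can speak with study staff and study physicians".
- IRB application, section 9.5: "Study participants will be provided with the phone number of the PI to contact with any concerns raised" by taking part in the program.

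Surveys at baseline, 6 and 12 months include side effects and symptoms (narrative 5.5; IRB application 13.10; survey items in the SAP). Section 5.5 has a study team member weigh each attender before every class. It does not have anyone ask an open question about adverse events at that point.

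**The concern.** A team can report only what it knows. A clock that starts at occurrence can expire before anyone in the study has heard of the event. Read literally, a late report is also a departure from the protocol, and deviations fall under the same clock.

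The request for reports has a separate weakness. In section 6.0 the participant must first judge that exercise was the cause, although the intervention is a very low-carbohydrate diet. A hospital admission that the participant does not connect with exercise lies outside that request.

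What is at stake is the completeness and timeliness of safety information. No sample size or test depends on it. The pilot is meant to inform a larger comparative trial, and an incomplete event record would be carried into that planning.

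**Working it through.** The only figure the plan states here is the 24-hour limit, so there is no calculation to reproduce. The check is how often the team has scheduled contact, and what the other routes add.

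**Step 1: time between classes.** Narrative 5.1 gives 16 core sessions, called weekly, in the first 6 months, then 8 sessions at one or two a month in the next 6. Half a year is 365.25 / 2 = 182.6 days.

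- Within a weekly run: 7 days.
- Core phase spread evenly: 182.6 / 16 = 11.4 days.
- Maintenance average: 182.6 / 8 = 22.8 days.
- Maintenance when monthly: 365.25 / 12 = 30.4 days, or 4.3 weeks.

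If the core sessions are strictly weekly, 182.6 / 7 − 16 = 10.1 weeks of the core period have no session.

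**Step 2: share of events known within 24 hours if learned of only at classes.** Assume events fall at random, every class is attended, and nobody reports between classes. The share is 1 day / interval, and the mean wait is interval / 2.

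| Schedule | Share within 24 h | Mean wait |
|---|---|---|
| Weekly run | 1 / 7 = 14.3% | 3.5 days |
| Core, spread evenly | 1 / 11.4 = 8.8% | 5.7 days |
| Maintenance, average | 1 / 22.8 = 4.4% | 11.4 days |

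Over the year the share is 24 / 365.25 = 6.6%. In a stretch of monthly classes it is 1 / 30.4 = 3.3%.

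If a fraction s of events is reported spontaneously within a day, the yearly share becomes s + (1 − s) × 6.6%. It runs from 6.6% at s = 0 to 100% at s = 1. The documents give no figure for s, so the table is a floor under full attendance. Missed classes lower it.

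**Step 3: the other routes.**

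| Route | What it adds | What it leaves open |
|---|---|---|
| Section 6.0 request | Asks that the study team be told | Only events caused by more activity |
| Section 5.1, activity item | Any adverse event | Telling the primary care provider alone is enough; no request that providers report back was found |
| Section 5.1, diet item | Staff and physicians are available | An offer, not a request to report |
| IRB application 9.5 | A telephone number between classes | Concerns tied to the program, so attribution is still needed |
| Surveys | Symptoms and side effects | First on-treatment survey at 6 months |

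**Step 4: what the symptom items can see.** The SAP's symptom checklist looks back one week and its free-text item one month (taken as 30 days). The two on-treatment surveys then cover 2 × 7 / 365.25 = 3.8% of the year by checklist and 2 × 30 / 365.25 = 16.4% by free text. IRB application 9.1 expects diet side effects mainly in the first weeks, which fall outside both windows.

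The question on hospitalization and major diagnoses stands in the SAP's Demographics block. Section 5.5 places sociodemographic questions at baseline.

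**The case against.** The strongest reply is that the protocol as a whole is broader than section 6.0. It invites contact about any adverse event, names diet side effects and offers staff contact, and gives the principal investigator's number. It also commits the team to report all adverse events (IRB application 9.10). Besides the symptom checklist, the surveys ask about medication changes at 6 and 12 months and about what got worse in the participant's health on the food plan. Interviews explore side effects. So the inference that the study asks only about exercise-related events does not hold: that describes one sentence of the safety plan.

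Four other strong readings also fail.

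- *The clock cannot be met, or most serious events will be reported late.* A participant may telephone the same day, and staff may know of a deviation at once. The supported statement is that compliance cannot be assured.
- *Section 9.9 sets a conflicting clock.* It states none, cites a policy not available here, and points back to the narrative. The two may agree.
- *The delay for non-attenders is unbounded.* The narrative expects some absentees to stay in telephone or email contact with the coach, attempts weigh-ins at 6 and 12 months, and mails the survey to those absent at session 15/16.
- *A planned safety conclusion will be invalid.* Safety is not a named outcome, and no statement of safety is promised.

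The consent pages and the standard operating procedures mentioned in section 6.0 were also not available, and reporting instructions may stand there.

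What remains is that none of the visible routes is a scheduled, open enquiry that brings every event to the study team. The surveys are too late and too short in recall for the early weeks.

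**Conclusion.** The point holds as a matter of safety ascertainment and should be corrected. The rule ties a 24-hour limit to occurrence in outpatients seen about every 1 to 4 weeks, with a possible gap of about 10 weeks if core classes are strictly weekly. Compliance cannot be assured. The 4% to 14% range is a worst case that rests on random timing, full attendance and no report between classes; the true share depends mainly on spontaneous reporting, which the documents do not quantify.

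Separately, the safety plan's own request is limited by cause, the broader request can be met without the study being told, and no class has a scheduled open question. Serious or diet-related events may be learned of late or missed, most plausibly in the first weeks. No estimate or test in the SAP changes.

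**What to change.** 1. In narrative 6.0, start the 24 hours when the study team becomes aware of the event. Confirm that this agrees with the policy cited in IRB application 9.9.
2. In 6.0, remove the restriction to events caused by increased physical activity. Align 6.0 and 5.1 so that the study team is always told of any adverse event, whether or not the primary care provider is told too.
3. Have the team member who already weighs participants ask one fixed question at each class: any hospital or emergency visit, new diagnosis or injury since the last class.
4. Add one item on the same events to the 6- and 12-month surveys, with an explicit window running from the previous survey. The existing Demographics question should not be reused as it stands: it has no time window and would collect lifetime history.
5. State that both surveys are mailed to non-attenders. Section 5.5 describes mailing only around session 15/16.

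The cost is protocol wording, one survey item, about a minute per participant per class, and more events to log.

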7.0 Privacy and Confidentiality

We will keep all subjects' records confidential to the extent provided by federal, state, and local law. All records will be kept in a secure area with restricted access available only to the research staff from the VA. Paper files will be stored in a locked filing cabinet and electronic files will be stored on a secure server. All surveys or paper documentation will be identified with a unique study ID number and will not include personal information.

If the results of this study are reported in any way, subjects will not be identified by name, photograph or any other means without consent. No information that identifies subjects will be released unless required by law. In our analysis of the data, we may have to share data with a third-party analysis company. In this event we will strip the data of any information that can identify subjects as individuals.

8.0 Communication Plan

This is a single-site study. It will be conducted at the Ann Arbor VA. We have full support for this pilot study from [name], Associate Chief of Staff/Ambulatory Care and Director of Primary Care/Associate Chief of Medicine at the AAVA (see attached letter).

We will obtain approval for any changes in the protocol, informed consent, and HIPAA authorization from the AAVA IRB prior to initiating the proposed change(s).

We will notify the AAVA IRB of any Serious Adverse Events, Unanticipated Problems, or interim results that may impact conduct of the study.

1.0 General Information

***Please enter the full title of your protocol. Be sure to click the ? to the right to ensure the protocol is correctly named.**

A Mixed Methods Pilot Study of a Low-Carbohydrate Diabetes Prevention Program Among Veterans with Prediabetes

***Please enter the Short Name you would like to use to reference the protocol:**

VA LC-DPP
 * This field allows you to enter an abbreviated version of the Protocol Title to quickly identify this study.

2.0 Add Department(s)

2.1 List departments associated with this protocol:

Primary Dept?	Department Name
	VAAAHS - CCMR

4.0 VA Ann Arbor Healthcare System IRB Application

Preliminaries

4.1 Is this IRB Protocol Federally Funded?

Yes No

4.2 What is the funding source for this IRB Protocol?

4.3 EXEMPTION from further IRB Review

4.4 Are you requesting EXEMPTION from further IRB review?

Yes No

4.18 Expedited Review

4.19 Are you requesting EXPEDITED IRB Review? (There is no need to request expedited review if you have requested an EXEMPTION from further IRB Review.) *NOTE: Expedited IRB Review does not indicate a faster review process, it simply means that review will take place outside of the convened IRB Meeting.*

Yes No

5.0 Summary Protocol Description

This section consists of a number of short questions that will provide an overview to the IRB and help guide you through the rest of the application.

5.1 PROTOCOL BASICS

5.2 Please include an ABSTRACT (Less than 500 words, organized under these headings: Objectives, Research Plan, Methods, and if a basic science study, Clinical Relevance)

Background / Objectives

Individuals with prediabetes can significantly reduce their risk of developing type 2 diabetes mellitus (T2DM) by achieving at least 5% body weight loss. Behavioral weight loss programs (MOVE!, TeleMOVE) are widely available within the Veterans Health Administration (VHA), but most participants do not achieve 5% body weight loss. This may be due, in part, to the programs' dietary advice, which teach participants to follow a low-fat, calorie-restricted diet. A low-carbohydrate diet may be one promising strategy to augment weight loss among Veterans with prediabetes. Our team previously adapted the Center for Disease Control and Prevention's National Diabetes Prevention Program—a group-based lifestyle change program similar to MOVE!—to teach participants to follow a very low carbohydrate diet (VLCD), defined as 20-35 non-fiber grams of carbohydrate per day. This pilot intervention was feasible, acceptable, and demonstrated preliminary weight loss effectiveness among patients of one academic medicine primary care clinic. It is unknown whether such a program may be feasible, acceptable, or effective for weight loss among Veterans with prediabetes.

The objectives of this single-arm mixed methods pilot study are (1) to test the feasibility and acceptability of a low-carbohydrate Diabetes Prevention Program (LC-DPP) among veterans with prediabetes and (2) to estimate weight loss among LC-DPP participants.

Methods

We will recruit up to 30 patients with body mass index ≥ 25 kg/m² and prediabetes (defined as hemoglobin A1c [A1c] 5.7-6.4%) from the Ann Arbor VA primary care clinic. Participants will be identified by chart review and invited to participate by postal letter. Individuals that do not opt-out of study contact will be screened for eligibility by telephone call. Interested and eligible participants will be invited to attend an in-person information session. During this session, they will receive information about the dietary intervention; written informed consent will be obtained at this time. Study participants will attend a total of 24 group-based classes over the course of 1-year. Body weight will be measured at each session. At baseline, 6-months, and 12-months, we will measure waist circumference and participants will be asked to complete a survey that includes measures of quality of life, mood, hunger, cravings, and self-reported physical symptoms. Primary outcomes will be feasibility (e.g., enrollment, retention) and acceptability (e.g., session attendance, qualitative feedback). Secondary outcomes will change in weight, achievement of $\geq 5\%$ body weight loss, and change in A1c. During semi-structured interviewed conducted at 6-months and 12-months, we will explore participants' experiences with the program, barriers to and facilitators of adherence to a low-carbohydrate diet, and perspectives on ways to improve the intervention.

Impact/Implications

Through this study, we will demonstrate the feasibility and acceptability of a LC-DPP among Veterans with prediabetes. These data will inform a large-scale comparative effectiveness trial of LC-DPP versus VA-MOVE.

